Clinicaltrials.gov ID: NCT03712410

Title: A Problem Solving Intervention for Hospice Caregivers

PI: [name]

Date of Document: December 20, 2022

Study Protocol and Data Analysis

Design

The study was designed as a randomized clinical trial with four groups. Hospice caregivers were randomly assigned to either to a group receiving standard hospice care with the addition of the PISCES intervention delivered face to face (Group 1) or a group receiving standard hospice care with the addition of the PISCES intervention delivered in a hybrid format (first session in person, remaining sessions via video) (Group 2) or a group receiving standard hospice care with the addition of the PISCES*plus* intervention delivered in a hybrid format (Group 3) or a group receiving standard hospice care with the addition of the PISCES*plus* intervention delivered entirely online (Group 4).

Setting and Participants

We partnered with Penn Homecare and Hospice Services. Penn Homecare and Hospice Services is an agency (part of the Penn Medicine system) that is Medicare and Medicaid-certified, accredited by the Joint Commission, licensed in the Commonwealth of Pennsylvania. It serves patients and families in Philadelphia, Chester, Delaware, Bucks and Montgomery counties mostly (total number of counties serves is 20) and is experiencing a growth over the years (20% increase in admissions over the past 5 years). The hospice component of the agency had a total number of 2,970 home admissions, an average daily census of 380 and an average length of service (LOS) of 68 days in 2016

Inclusion criteria for caregivers were the following:

- enrolled as a family/informal caregiver of a hospice patient
- 18 years or older
- with access to a standard phone line or Internet and computer access at home
- without functional hearing loss or with a hearing aid that allows the participant to conduct telephone conversations as assessed by the research staff (by questioning and observing the caregiver)
- no or only mild cognitive impairment—mental status will be assessed using the Short Portable Mental Status Questionnaire;¹ individuals with a score of less than seven (i.e., more than three errors) will be excluded, similar to other studies involving this instrument.
- speak and read English, with at least a 6th-grade education

Enrollment

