The hospice admissions staff presented the research opportunity to caregivers upon admission, asking them if they agree to be contacted by the research staff to find out more about the study. The admissions staff then forwarded contact information for caregivers willing to learn more about the study to the research team if they fulfilled the eligibility criteria. The interventionist called and scheduled the initial visit. The interventionist visited the caregiver, discussed the project, obtained informed consent from the caregiver, and documented demographic data. The interventionist opened a numbered sealed envelope, prepared by the team in advance, which assigned caregivers to one of the three groups. This approach ensured that consent is obtained prior to group assignment and caregivers consent to participate in the study, regardless of group assignment. Randomization was stratified by site. Furthermore, we followed a block randomization approach to ensure that treatment groups are not imbalanced with respect to time of the year as season (e.g., holidays) may have an effect on some of the psychometric measures. Upon consent, caregivers were asked to review and prioritize common caregiver concerns using a checklist, as the intervention will focus on the top three concerns or problems. Following this visit, a research assistant called the caregiver to conduct the baseline assessment (including anxiety, quality of life, caregiver reaction and problem solving inventory) over the phone. The research assistant was blinded to the caregiver's group assignment to

eliminate any potential bias. While the pre- and post assessments were conducted by the research assistant over the phone, the consent visit, actual intervention visits/ video-calls and exit interviews were delivered by an interventionist.

Group 1: PISCES delivered face to face

Before departing, the interventionist tentatively scheduled the upcoming three face-to-face visits for caregivers, and leave a manual on problem-solving designed for the lay audience based on “Solving Life’s Problems” by Nezu and D’Zurilla who developed the PST theoretical frameworkⁱⁱ with a special emphasis on hospice and hospice specific examples. The three intervention visits were scheduled with a suggested timeline between days 5 and 18 of the hospice admission.

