During the second visit (suggested timeline 11-13 days after hospice admission) the interventionist covers steps three and four of the ADAPT model. Step three encourages caregivers in being creative and generating alternative solutions. This step involves brainstorming possible solutions to the identified problem, encouraging caregivers to brainstorm many alternatives, defer judgment on these alternatives until a later stage of the intervention and think of a wide range of possible strategies (general) and tactics (more specific). Step four focuses on predicting the consequences and developing a solution plan. This step involves evaluating alternatives and choosing the one that is most likely to effectively solve the identified problem. Making effective decisions involves screening out obviously ineffective solutions, predicting possible consequences, evaluating solution outcomes, and identifying effective solutions/developing a solution plan.

The third visit (suggested timeline 16-18 days after hospice admission) focuses on step five, namely trying out the solution plan and determining if it works. The general goal is to systematically evaluate the solution that caregivers implemented as a result of the previous steps to determine if it was effective in solving (or improving) the identified problem.

Group 2: PISCES delivered in a hybrid format

In this group, participants received the PISCES intervention in three sessions; however, the first session was delivered face to face and the other two via video. The three intervention sessions

were scheduled with a suggested timeline between days 5 and 18 of the hospice admission as in Group 1.

The first session took place in person (suggested timeline 5-7 days after hospice admission) and included an explanation of the purpose of the visit/call, and confirmation of the three specific problems that the caregiver had selected from the concern list. During the first session, the interventionist worked on steps one and two of the ADAPT model of the PST, namely "Attitude" and "Defining the Problem and Setting Realistic Goals." After the first session where the in person encounter allowed for the establishment of rapport between the interventionist and the caregiver, the second session (suggested timeline 11-13 days after hospice admission) and the third session (suggested timeline 16-18 days after hospice admissions) were conducted via live videoconferencing.

Group 3: PISCESplus delivered in a hybrid format

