After all three intervention sessions were completed, a research assistant (blinded to the group assignment) called caregivers in all four groups for a post-intervention assessment of anxiety, depression, quality of life and problem solving inventory. This segregation of responsibilities and the blinding of the research assistant to the group assignment aimed to minimize any potential bias. Caregivers received a phone exit interview a few days after the last intervention visit and post intervention assessment phone call.

Treatment Fidelity

To ensure treatment fidelity to the planned interventions, we used the training and treatment fidelity manual refined during previous work. The guide details the training of research staff, the nature of each of the three intervention sessions, and the protocol for administering each of the evaluative instruments. All face to face visits and all video-calls were audio-taped by the research staff and a randomly chosen sample of 10% of all sessions were studied. Thus, the integrity of the intervention protocol was systematically assessed via reviews of audio recordings of these sessions. Tapes were rated by the principal investigator (PI) for overall adherence to the protocol and inclusion of all required elements, as well as to confirm that no contamination took place (e.g., a case where the interventionist provided specific advice for a problem without allowing the caregiver to review and select an option). The research team was required to make adjustments if interventions were violating the intervention protocol. The intervention manual included our intervention monitoring tools (IMTs) that were refined based on recommendations by Radziewicz et al^{iv} to help assure fidelity in individualized intervention studies.

Measures

Measures for Specific Aims 1 and 2:

Generalized anxiety disorder (GAD-7): The GAD-7 is a brief, valid and efficient tool for screening for anxiety and assessing its severity in clinical practice and research. The GAD-7 has been tested and demonstrated high levels of reliability and validity.^v The total score is calculated by assigning scores of 0-3 for each of the seven items. Scores of 5, 10, and 15 are taken as the cut off points for mild, moderate, and severe anxiety, respectively.

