	Video	Telephone	Video	Video	Video	Telephone	Telephone
Delivered by:	I	RA (blinded to group assignment)	I	I	I	RA (blinded to group assignment)	RA

I=Interventionist; RA=Research Assistant; F2F=Face-to-Face

Measures for Specific Aim 3

We conducted exit interviews with caregivers in all three groups. Caregivers in Group 1 were asked to provide general feedback about the PISCES intervention. Exit interviews with caregivers in Groups 2, and 3 also assessed caregivers' perceptions of the hybrid delivery platform (face to face and video sessions); caregivers in Groups 3 and 4 were further asked to provide feedback on the positive reappraisal aspects of PISCESplus. Interviews were carried out by the research coordinator and audio-taped based on an interview protocol aiming to examine caregivers' perceptions and satisfaction. Interview questions pertained to satisfaction with this form of interaction, barriers and facilitators to the use of video, and confidence in using this form of interaction, lasted 20 to 30 minutes. The interviews were digitally recorded and transcribed. The QSR Nvivo11 software was used to manage and interpret the data. This software facilitates the organization of emerging ideas, to search and explore in context, and to seek patterns.

Measures for Specific Aim 4:

We conducted a cost analysis and we utilized the demographic data collected on enrollment in the study to allow for comparisons between the groups. These include hospice admission date and diagnosis, patient and informal caregiver age and sex, race, informal caregiver employment status, education and income range, relationship of informal caregiver to patient, and residence of the informal caregiver. We also equipment costs (including equipment price and depreciation), and training costs based on time to train research staff in the use of videoconferencing. The participating hospice agency also furnished the research team with the following client-level data to estimate resource use and costs:

- direct care time for scheduled visits by type of professional
- travel distance and time spent traveling for scheduled visits by type of professional
- direct care time for after-hour calls and visits by type of professional
- travel distance and time spent traveling for after-hour visits by type of professional

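### Four groups are said to be randomised, but the only allocation step described covers three, so comparisons that include Group 4 cannot be verified as randomised

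*Combined protocol and SAP*

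**What the plan says.** The Design section states: "The study was designed as a randomized clinical trial with four groups". It lists Group 4, PISCESplus entirely online, among the groups to which caregivers were randomly assigned.

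Enrollment gives the only mechanism. First, "The interventionist visited the caregiver, discussed the project, obtained informed consent from the caregiver, and documented demographic data". Then, "The interventionist opened a numbered sealed envelope, prepared by the team in advance, which assigned caregivers to one of the three groups". Randomisation was stratified by site, and "we followed a block randomization approach to ensure that treatment groups are not imbalanced with respect to time of the year". No allocation ratio or block size is given, and nothing is said about when Group 4 opened or how it was filled. The data-collection table (Table 1: Timeline for data collection) shows Group 4's first, demographic contact as video.

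The remaining text counts groups both ways:

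- **Four groups.** The blinded assistant "called caregivers in all four groups for a post-intervention assessment". In Measures for Specific Aim 3, "caregivers in Groups 3 and 4 were further asked to provide feedback on the positive reappraisal aspects of PISCESplus". The Specific Aim 4 analysis compares costs across four groups.
- **Three groups.** Measures for Specific Aim 3 also says: "We conducted exit interviews with caregivers in all three groups". The Specific Aim 4 analysis opens by naming three intervention groups. Other Measures limits the video-quality form to Groups 2 and 3, although every Group 4 session is by video. The Specific Aim 3 analysis ties the reappraisal modules to Group 3 only.

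For Specific Aims 1 and 2 the plan is an ANCOVA with baseline score, site and patient death as covariates. Specific Aim 2 has two comparisons at 0.025 each. The results use unadjusted rank tests: Kruskal-Wallis on four groups (Table 2), and Wilcoxon tests between (Table 3) and within (Table 4) columns labelled Traditional and Online. Group 2 sits under Traditional in the participant-characteristics table, yet its Group 2 section says "the first session was delivered face to face and the other two via video".

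**The concern.** A between-group test has its usual causal reading only if the arms come from one randomised schedule or from schedules running at the same time. Blocking by time of year protects only arms filled from the same blocks. If Group 4 was filled at another time or by another route, differences in season, case mix or recruitment source would enter Table 2 and the pooled column of Table 3, and the rank tests adjust for none of them. Group 4 is also the only fully online arm, so any claim for that format depends on how it was filled.

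**Working it through.** **1. The text.** Four randomised groups (Design) and an envelope for three (Enrollment) cannot both describe the whole trial. The envelope step follows a home visit; Group 4's corresponding contact is by video. The mixed wording elsewhere looks like partly updated text. It shows that Group 4's allocation is inconsistently and incompletely described, not what the allocation was. Specific Aim 2's two comparisons do not settle it: they fit Group 3 against Groups 1 and 2, or Groups 3+4 against each.

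**2. Group sizes** (participant-characteristics table). The total is 154 + 152 + 154 + 63 = 523. Groups 1-3 fit 1:1:1 (chi-square 0.017, 2 df, p = 0.99). Equal four-way allocation would give 523/4 = 130.75 each; the chi-square is 46.8 on 3 df, p = 4e-10. This excludes only an equal ratio. 154/63 = 2.4, so an unstated ratio of about 2.4:1, or an arm opened later, would also give 63.

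**3. Baseline comparison** (Pearson chi-square, no continuity correction, from the printed counts). The printed four-group values reproduce: care-receiver sex 0.0023 (printed 0.0023) and residence 0.0488 (printed 0.0488).

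*Care-receiver sex*, female: 75/144, 83/142, 64/133 and 47/62.
- Within Groups 1-3: chi-square 3.01, 2 df, p = 0.22.
- Group 4 against Groups 1-3, 47 female and 15 male against 222 and 197: chi-square = 481 × (47×197 − 15×222)² / (62 × 419 × 269 × 212) = 11.41, p = 0.0007.
- Difference: 75.8% − 53.0% = 22.8 points; standard error 5.96; 95% CI 11 to 35.

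The participant table prints 23 p-values. Multiplying by 23 gives 0.017 for Group 4 against the rest, but 0.0023 × 23 = 0.053 (0.054 unrounded) for the four-group test.

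Sex is missing for 460 − 419 = 41 (9%) in Groups 1-3 and for 1 of 63 in Group 4. In the extreme case least favourable to the finding (all 41 female, the one male) the split is 263/460 (57.2%) against 47/63 (74.6%), p = 0.008, or 0.19 after multiplying by 23.

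*Residence*: Group 4 against the rest p = 0.006, within Groups 1-3 p = 0.68; 0.006 × 23 = 0.14.

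*Not relied on*: diagnosis is recorded for 163 of 523, so 360/523 (69%) is missing. The bereavement gap (4/63 against 136/448) may arise after allocation.

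*Against a separate population*: the printed p-values for baseline age, GAD-7, PHQ-9 and quality of life run from 0.42 to 0.57.

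**4. What Table 3 compares.** The participant-table header places Group 3 and the column of 63 under Online. Weighting the Table 2 mean changes by enrolled numbers (follow-up numbers are not given):

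| Change | Groups 3+4, (154·m3 + 63·m4)/217 | Table 3 Online | Groups 1+2, (154·m1 + 152·m2)/306 | Table 3 Traditional |
|---|---|---|---|---|
| GAD-7 | −2.05 | −2.03 | −2.02 | −2.04 |
| PHQ-9 | −1.91 | −1.91 | −2.13 | −2.15 |
| CQLI-R | 0.53 | 0.54 | 0.96 | 0.96 |

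So Online is Groups 3+4 and Traditional is Groups 1+2, which is PISCESplus against PISCES. Hybrid delivery was assigned to 154/217 = 71% of Online and 152/306 = 50% of Traditional.

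**5. Effect on the printed means.** Online minus Traditional as printed, then with Group 3 alone in place of Online: GAD-7 +0.01, then −0.23; PHQ-9 +0.24, then +0.28; CQLI-R −0.42, then −0.69. The largest shift is 0.27 points. The printed p-values are 0.1860, 0.2752 and 0.6233 in Table 2 and 0.5638, 0.9848 and 0.9169 in Table 3.

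**The case against.** The Design section does assert randomisation and names Group 4, so the three-group wording may simply be left over from an earlier design. That stands: the comparisons cannot be verified as randomised, which is weaker than saying they were not.

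A reader might infer from the group size and the baseline differences that Group 4 was not randomised. The documents do not support that. No ratio is stated, so 63 rules out only equal allocation, and an arm added later could still have been randomised. The sex difference survives multiplicity only in the Group 4-against-rest contrast. That contrast is reasonable because the text singles out Group 4, but it is a choice, and 9% of Groups 1-3 lack the item. Residence does not survive, and the clinical baseline scores agree.

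A reader might also infer that the results would change without Group 4. Individual data and follow-up numbers are not given, and tests approximated from means and SDs do not track the printed rank tests: for PHQ-9 at enrolled numbers, such a test gives about 0.14 for four groups against the printed 0.2752. No such re-test should be relied on.

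Finally, Table 4 is a within-group comparison and never rested on randomisation. It is affected only in that its Online column may mix two populations.

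**Conclusion.** The contradiction is in the current text, and the pooling follows from the table header and the arithmetic; both are firm. That Group 4 was a later or separate cohort is consistent with its size and with a 23-point difference in care-receiver sex, but remains unproven. Until the allocation is documented, the Table 2 four-group test and the Table 3 contrast cannot be verified as randomised. Group 1 against 2, Group 3 against 1 and Group 3 against 2 stand whatever the answer.

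Separately, and independently of Group 4's allocation, Table 3's label is wrong as written: the contrast is PISCES against PISCESplus, with hybrid caregivers in both columns.

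No printed between-group test is significant, so no positive claim falls. What is at stake is how Tables 2 and 3 may be read and what can be said about fully online delivery. The baseline working assumes that the printed counts are right; the pooling check assumes follow-up roughly in proportion to enrolment.

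**What to change.** 1. State from the trial records how, when and in what ratio Group 4 was allocated. Reconcile Design, Enrollment, the post-intervention assessment paragraph, the Specific Aim 3 measures and analysis, Other Measures and the Specific Aim 4 analysis, including the mode of the consent and demographics contact.
2. Report the planned ANCOVA for Group 1 against 2, Group 3 against 1 and Group 3 against 2. State whether Specific Aim 2's two comparisons mean Group 3 alone or Groups 3+4.
3. If Group 4 was randomised, compare it only with concurrently randomised caregivers, using that ANCOVA. If it was not, or this cannot be documented, remove it from the between-group tests and pooled columns, give it its own column, and label any comparison non-randomised. Adjust such a comparison for baseline score and pre-allocation characteristics such as care-receiver sex and residence, and for site only where sites overlap. Use patient death only as a sensitivity analysis unless it is shown to precede allocation.
4. Relabel Table 3 and the columns of Table 4 as PISCES and PISCESplus, and note that delivery mode also differs between them.

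The cost is one allocation paragraph, wording corrections, the analysis already planned and, depending on step 1, a re-run of three tables, with no new data. The downside is that Group 4's 63 caregivers may leave the randomised contrasts, and the evidence for fully online delivery may become observational.

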Demographic data: Standard demographic data were collected on patients and caregivers, including age, gender, nativity, education level, marital status, occupation, patient's diagnosis, relationship to patient, location of residence (residing with patient or not), estimate of average time spent on caregiving activities per week, impact on employment (whether caregiver had to decrease work hours or give up employment) and perceived income adequacy (having a comfortable income, having just enough to get by, not having enough to get by). Furthermore, if the patient dies during the subject's participation, that will be recorded along with the date of death (to allow for calculation of timing of death in the context of subject's days in the study).

Table 1 demonstrates the timeline for the collection of these measures.

Table 1: Timeline for data collection

	1 Baseline	2 Pre- Interventio n Assessme nt	3	4	5	6 Post-intervention Assessment	7 Exit interview
Group 1 PISCES delivered face to face Delivered by:	Demo- graphic data F2F I	Measures (PHQ-9, CQLI-R, PSI, GAD- 7) Telephone RA (blinded to group assignment)	PST Session 1 F2F I	PST Sessio n 2 F2F I	PST Session 3 F2F I	Measures (PHQ-9, CQLI-R, PSI, GAD-7) Telephone RA (blinded to group assignment)	Telephon e RA
Group 2 PISCES delivered in a hybrid format	Demo- graphic data F2F	Measures (PHQ-9, CQLI-R, PSI, GAD- 7) Telephone	PST Session 1 F2F	PST Sessio n 2 Video	PST Session 3 Video	Measures (PHQ-9, CQLI-R, PSI, GAD-7) Telephone	Exit interview Telephon e

Delivered by:	I	RA (blinded to group assignment)	I	I	I	RA (blinded to group assignment)	RA
Group 3 PISCESplus delivered in a hybrid format	Demo-graphic data	Measures (PHQ-9, CQLI-R, PSI, GAD-7)	PST+ positive reappraisal Session 1	PST+ positive reappraisal Session 2	PST+ positive reappraisal Session 3	Measures (Measures (PHQ-9, CQLI-R, PSI, GAD-7)	Exit interview Remove video
Delivered by:	I	RA (blinded to group assignment)	I	I	I	RA (blinded to group assignment)	Telephone RA
Group 4 PISCESplus delivered online	Demo-graphic data	Measures (PHQ-9, CQLI-R, PSI, GAD-7)	PST+ positive reappraisal Session 1	PST+ positive reappraisal Session 2	PST+ positive reappraisal Session 3	Measures (Measures (PHQ-9, CQLI-R, PSI, GAD-7)	Exit interview Remove video

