The primary analyses focused on examining differences between treatment groups in terms of caregiver outcomes during the time of intervention. Changes in caregivers’ scores from baseline to post-treatment will be analyzed using analysis of covariance, with baseline score, site, and whether the caregiver’s patient has died, as covariates. Separate models were run for each outcome (caregiver quality of life, anxiety, depression, and problem-solving ability). For Specific Aim 1 (SA1) to assess the equivalence between PISCES F2F and PISCES in hybrid format, a confidence interval approach was used on the ANCOVA model, with a two-sided 5% level of significance. If the CI of the difference between the two groups falls within the pre-specified range of equivalence, the two interventions will be considered equivalent.^{xiii xiv} The range of equivalence is defined between $-\Delta$ and $+\Delta$. The clinically informed Δ s for the primary outcomes are: CQLI-R = 1.0; GAD-7 = 1.75; PHQ-9 = 2.0; PSI = 2.5, respectively. The analyses of equivalence will be on a per-protocol basis and will be supplemented by secondary sensitivity intent-to-treat analyses.⁵⁵

The analyses for Specific Aim 2 (SA2) focus on pair-wise comparisons between PISCES*plus* and the other treatment groups. A significance level of $\alpha=0.025$ for each comparison was used to account for the multiple (2) comparisons and assure an overall significance level of no more than 0.05 for each outcome. These analyses of superiority was on an intent-to-treat basis, using

multiple imputation to address missing data. ANCOVA and chi-square tests were used to determine whether attrition had an impact on sample composition. Specifically, analyses were computed on baseline demographic characteristics, as well as baseline outcome measures, to determine whether participants who completed all phases of data collection were initially different when compared with persons who did not complete the intervention. Data were analyzed using the Stata statistical package.

Data Analysis for Specific Aim 3

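### The primary ANCOVA adjusts for patient death, an event after allocation; this hardly moves contrasts among Groups 1 to 3 but could matter for any contrast with Group 4

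*Combined protocol and SAP*

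**What the plan says.** Under Data Analysis for Specific Aims 1 and 2, change from baseline is analysed by ANCOVA, one model per outcome. The covariates are baseline score, site and whether the "patient has died, as covariates". No reason is given for the death term, no cut-off date defines it, and no model without it is planned.

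Four other places fix its timing:

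- The inclusion criteria require a person "enrolled as a family/informal caregiver of a hospice patient", so the patient should be alive at entry.
- Under Enrollment, allocation takes place at the consent visit: "The interventionist opened a numbered sealed envelope, prepared by the team in advance, which assigned caregivers to one of the three groups". The baseline telephone assessment follows that visit.
- Under Measures (demographic data): "if the patient dies during the subject's participation, that will be recorded along with the date of death".
- The follow-up call has no fixed day. The text before Treatment Fidelity begins "After all three intervention sessions were completed, a research assistant", and the Group 1 section calls the session timetable a guideline to be adapted to each caregiver.

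The ANCOVA serves Aim 1, "to assess the equivalence between PISCES F2F and PISCES in hybrid format" (Group 1 against Group 2), and Aim 2, two PISCESplus comparisons at 0.025 each. The plan does not say which PISCESplus arm, or arms, Aim 2 uses.

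**The concern.** A covariate measured after allocation is safe only if allocation cannot influence it. It is reasonable to suppose that caregiver training does not change how long a hospice patient lives. The covariate, however, is death within a window, and the window closes when that caregiver finishes three sessions. If one delivery mode takes longer to complete, more deaths fall inside its window even when survival is identical. Adjustment would then remove part of a delivery effect or introduce bias, and the adjusted difference would no longer be the plain effect of allocation that an intention-to-treat analysis seeks.

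The plan offers no protection against this, and Table 1 shows one arm with a very different bereaved share. What is at stake is the interpretation of contrasts that involve that arm.

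**Working it through.** **Inputs (Table 1, participant characteristics, Caregiver Status).** Bereaved / active: Group 1 43 / 107, Group 2 47 / 102, Group 3 46 / 103, Group 4 4 / 59.

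**1. Reproduce the printed figures.** Shares are 43/150 = 28.7%, 47/149 = 31.5%, 46/149 = 30.9% and 4/63 = 6.3% (printed as 6.4%). Overall, 140/511 = 27.4%. Pearson chi-square on the 4 × 2 table is 16.35 on 3 df, p = 0.00096, which matches the printed 0.0010.

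**2. Locate the imbalance.**

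- Groups 1 to 3 alone: chi-square 0.32 on 2 df, p = 0.85.
- Group 1 minus Group 2: −2.9 percentage points (95% CI −13.3 to 7.5).
- Group 4 minus Group 3: −24.5 percentage points (95% CI −34.1 to −15.0).
- Groups 1 to 3 pooled: 136/448 = 30.4%. Gap to Group 4: 0.304 − 0.063 = 0.24.

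The imbalance comes entirely from Group 4.

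**3. Effect on a contrast.** Let *b* be the difference in outcome between bereaved and active caregivers. Ignoring small differences in the other covariates, removing the death term shifts the contrast of arms A and B by *b* × (pA − pB). The documents give no *b*; I assume 1 to 5 points.

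| Contrast | Difference in share | Size of shift, *b* = 1 to 5 |
|---|---|---|
| Group 1 v 2 (Aim 1) | 0.029 | 0.03 to 0.14 |
| Group 3 v 1 | 0.022 | 0.02 to 0.11 |
| Group 3 v 2 | 0.007 | 0.01 to 0.03 |
| Group 4 v 3 | 0.245 | 0.25 to 1.23 |
| Group 4 v Groups 1 to 3 pooled | 0.240 | 0.24 to 1.20 |

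**4. Put these on scale.** The Aim 1 margins are 1.0 (CQLI-R), 1.75 (GAD-7), 2.0 (PHQ-9) and 2.5 (PSI). To move Group 1 v 2 by a whole margin, *b* would have to be 1.0/0.0288 = about 35 points on CQLI-R, or 1.75/0.0288 = about 61 on GAD-7. GAD-7 runs only from 0 to 21. For Group 4, the crude GAD-7 change in Table 2 differs from Group 3 by −1.52 − (−2.27) = 0.75 points, and *b* = 3 alone would shift that contrast by 0.74.

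**5. Precision given up by dropping the term.** Assume a GAD-7 residual SD of 3.8 without the death term (not in the documents), so variance 14.44. Bereavement variance in Groups 1 to 3 is 0.304 × 0.696 = 0.21. The SE ratio is √[14.44 / (14.44 − 0.21*b*²)], which is 1.007, 1.030 and 1.073 for *b* = 1, 2 and 3: about 1%, 3% and 7% wider.

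For Group 4 v 3 fitted on those two arms, even this gain is doubtful. The squared correlation of arm and bereavement is (46 × 59 − 103 × 4)² / (50 × 162 × 149 × 63) = 0.070, so including the term inflates the SE by √(1/0.930) = 1.037. That roughly cancels the gain at *b* = 2.

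**The case against.** The strongest reply is that patient death is prognostic, is very unlikely to be caused by caregiver training, and may legitimately be adjusted for to gain precision. If allocation affects neither death nor its timing, that is correct and the planned model does no harm. The documents give no completion times, and all four arms share the same suggested schedule (days 5 to 18). Face-to-face and hybrid arms have nearly the same bereaved share, so moving two of three sessions to video made no visible difference. The timing path is plausible, not demonstrated.

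A reader might infer from 6.4% against about 30% that online delivery changed the chance of bereavement. The documents do not support that. Table 1 does not date the Bereaved row; reading it as death during participation is an inference from the entry criterion and the rule for recording deaths. Group 4 also differs on traits that allocation cannot alter: dementia in 13 of the 23 with a recorded diagnosis (56.5%, against 3.9% to 6.8%), and male care receivers 24.2% against 41.6% to 51.9%. It has 63 participants against 152 to 154, and several sections still speak of three groups. Later, non-concurrent enrolment would fit, but the documents do not state it. If case mix explains the gap, bereavement partly stands in for it, and dropping the term without adjusting for case mix could make a Group 4 contrast worse. This point stands and shapes the fix.

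Three further inferences would also go too far:

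- A Group 4 contrast does not rest on four bereaved caregivers. A main-effects ANCOVA estimates one common coefficient, from 140 bereaved caregivers with four arms or 50 with Groups 3 and 4. Only an interaction model would rest on four.
- No reported result is shown to be biased. Tables 2 to 4 use rank tests, and no death-adjusted estimate appears.
- The Aim 1 primary analysis is per-protocol, so it never targeted the effect of allocation alone.

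**Conclusion.** The concern holds as a matter of design, with limited numerical reach. The primary model conditions on an event that arises after allocation, over a window whose length the intervention schedule can influence, and the plan neither justifies nor dates it.

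For contrasts among Groups 1 to 3, including all of Aim 1, the observed imbalance moves the estimate by at most about 0.14 points, so the equivalence conclusion is not threatened by this. For any contrast with Group 4 the shift is about 0.24 to 1.2 points against Groups 1 to 3, which could be material beside a crude GAD-7 difference of 0.75 from Group 3. Whether such a contrast belongs to Aim 2 is left open: two comparisons at 0.025 fit Group 3 against Groups 1 and 2, yet Group 4 is also a PISCESplus arm.

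These sizes rest on an assumed bereavement effect of 1 to 5 points and on reading the Bereaved row as death during participation. The cause of the Group 4 gap is unknown. The change is worth making because it is cheap and removes a dependence that the plan cannot defend from its own text.

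**What to change.** - **Primary model.** Adjust for baseline score, site and characteristics fixed before allocation, without patient death. State that the effect is estimated whether or not the patient dies. The baseline score is strictly taken after allocation, but before any session and by a blinded assessor, so it should stay.
- **Case mix.** Candidates are patient diagnosis where available and care receiver gender. Table 1 has diagnosis for only 51 + 44 + 45 + 23 = 163 of 523 participants, so its missing values need a stated method.
- **Deaths.** Report them by group from the recorded dates, counted from allocation. The baseline call is not a suitable cut-off, because it follows allocation; adjusting for deaths before that call would still adjust for a post-allocation event.
- **Sensitivity analysis.** Keep the planned death-adjusted model, with the date by which death is counted written down.
- **Group 4.** Show both models for any contrast that includes it, since the imbalance may partly reflect case mix. Say which Aim 2 comparisons include Group 4 and whether it was randomised concurrently.

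The cost is SAP wording and one extra model per outcome; the plan already provides for recording dates of death. The price in precision among Groups 1 to 3 is an SE about 1%, 3% or 7% wider for an assumed 1, 2 or 3-point bereavement effect on GAD-7, with an assumed residual SD of 3.8.
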